7.1.2 Handling of Missing Values

All analysis will be based on available data. No imputations will be made for missing data unless otherwise specified. Missing baseline measurements may be replaced with the patient's value recorded during the latest visit before study treatment administration, if applicable.

7.1.3 **Pooling of Sites**

Data will be pooled from up to 8 sites for this analysis. The justification for pooling is made on a clinical basis (Meinert, 1986). The basis for pooling comes from three critical factors: 1) The study sites must implement one common protocol. 2) The sponsor must provide very close monitoring of study site compliance. 3) The study sites must use common data collection procedures.

7.2 PATIENT CHARACTERISTICS

7.2.1 Patient Disposition and Enrollment

Complete accounting of patient participation (from entrance into the study through final visit) in the study will be presented in the summary table for patient disposition. The table will include the following: total completing the study, number of patients who

This Document is Company Confidential Page 12 of 28 withdrew, and reasons for early withdrawal. The table will be summarized by cohort and pooled across cohorts. Patient disposition will also be summarized by visit within each cohort.

The number and percentage of enrolled patients enrolled at each site will be summarized by cohort and pooled across cohorts. The number and percentage of patients who are included in each analysis population will also be presented by cohort and pooled across cohorts.

A listing of patient disposition will be provided.

7.2.2 Demographic Characteristics

Patient demographics, such as age, sex, race and ethnicity will be summarized with descriptive statistics.

A listing of patient demographics will be provided.

7.2.3 Protocol Deviations

All instances of failure to comply with the study protocol will be tracked during the study. Prior to database lock the sponsor will decide whether any patients or any individual parameters pertaining to a patient will be excluded from the safety and efficacy evaluations when the protocol deviation is considered to have a negative impact on scientific aspects and interpretation of the study results.

All protocol deviations will be listed.

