3. STUDY DESIGN

3.1 OVERVIEW

This is an open-label safety study of stereotactic, intracranial injection of SB623 cells in patients with hemiparesis from stable ischemic stroke who have remained stable during the prior 3 weeks (based on NIHSS assessments at weeks -3 and -1). While primarily a safety study, efficacy parameters will also be evaluated. Three cohorts will receive escalating singe doses of SB623, which are to be stereotactically implanted into grey or white matter sites adjacent to the infarct region. One burr-hole craniostomy will be created, and cells implanted using 3 needle tracks with 5 cell deposits for each track at varying depths around the damaged area. Cell implantation will be standardized as to volume (20 μ L/deposit) and rate (10 μ L/min), with spacing between each implant of approximately 5-6 mm. Each deposit is expected to take approximately 2-3 minutes, with each needle track being completed within 15 minutes. Each cohort will consist of 6 patients defined by an increasing total number of cells implanted. Safety will be monitored by the Investigator, Principal Monitor, Medical Monitor, and an external Data Safety Monitoring Board (DSMB). For the first cohort, a single patient will first be dosed, then evaluated over a 2 week period for safety prior to dosing the next member of the cohort. This 2-week interval will continue between each of the remaining members of the cohort. If the safety profile is acceptable for a cohort, and after review by the DSMB, the first patient in each subsequent cohort will be dosed, beginning 4 weeks after dosing of the last patient of the prior cohort. For the second and third patients in each of the subsequent cohorts, there will be an interval of 2 weeks after the prior patients prior to further enrollment.

SanBio Incorporated Protocol SB-STR01

A dose-limiting toxicity (DLT) will be defined as any grade 3 or 4 events which are at least possibly related to study product or administration procedure. If the first patient in a cohort has a DLT attributable to the SB623 cells, then no further patients will be dosed in that cohort until a comprehensive evaluation has been conducted. If 2 of 6 patients in a cohort have a DLT attributable to the SB623 cells, then no further patients will be dosed in that or other higher-dose cohorts. Each DLT will be evaluated by the DSMB. The DSMB shall be the final arbitrator for attributions.

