4. ANALYSIS SETS

4.1 EFFICACY POPULATION

Intent-to-Treat (ITT): The intent-to-treat (ITT) population will include all enrolled patients. Enrolled patients are patients who meet all inclusion/exclusion criteria and qualified for the study or who were granted exceptions to selected inclusion/exclusion criteria, meet all other inclusion/exclusion criteria and qualified for the study, including those who were discontinued from the study or withdrawn for any reason. The ITT population will be used in all efficacy analyses.

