4.2 SAFETY POPULATION

Safety Population: The safety population will include all enrolled patients who have received treatment with SB623 and who have any post-baseline data. The safety population will be used in all safety analyses.

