7.1 GENERAL CONSIDERATIONS

Descriptive statistics for continuous variables will include the count of patients (N), mean, standard deviation (SD), median, minimum, maximum and confidence interval (CI, as appropriate); for categorical variables, descriptive statistics will include the number and percentage of patients for each category. Unless otherwise indicated, percentages will be calculated based upon patients with non-missing data as the denominator. When appropriate data will be summarized by dose and visit/time point.

In summary and analysis tables of continuous variables, the minimum and maximum statistics will be presented to the same number of decimal places as the original data. The mean, median, quartiles, and 2-sided 95% confidence interval (CI) will be presented to 1 more decimal place than the original data. The standard deviation and standard error will be presented to 2 more decimal places than the original data.

Analysis of the efficacy endpoints (primary, secondary, and exploratory) will be based on the ITT population defined in Section 4.1. Assessments of tolerability and safety will be based on the safety population defined in Section 4.2.

There are no changes in the protocol-specified analyses.

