7.1.1 Hypotheses and Decision Rules

The study is a Phase 1/2A study, with the primary objective of safety and tolerability, and is therefore not powered for multiple efficacy endpoints. All efficacy evaluations are exploratory and no adjustment for multiplicity will be performed. Hypothesis testing of each endpoint will be independently carried out at the 5% (2-sided) significance level.

All statistical analyses will be performed using SAS[®] v9.2 or higher.

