7.5 INTERIM ANALYSIS

One interim analysis is planned, which will be performed when the last patient enrolled in the study, has completed their Month 6 visit. This interim analysis will be based on the Month 6 data and will include all tables, listings, and figures.

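### SAP 7.2.3 lets the sponsor drop patients or single values for protocol deviations, contrary to the SAP's own ITT and Safety rules, with no fixed criteria and no requirement to decide without sight of outcomes

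*SAP*

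**What the plan says.** Before database lock, SAP 7.2.3 provides, "the sponsor will decide whether any patients or any individual parameters pertaining to a patient will be excluded from the safety and efficacy evaluations". The condition is that the deviation is thought to damage the science or the interpretation of the results. The section lists no qualifying deviation types, names no reviewer independent of the sponsor, does not require the decision to be made without sight of outcomes, and does not say which lock is meant. It does require all deviations to be listed.

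The analysis-set sections say something different:

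- SAP 4.1 puts all enrolled patients in the ITT set, including those "who were granted exceptions to selected inclusion/exclusion criteria" and those who withdrew. It adds: "The ITT population will be used in all efficacy analyses".
- SAP 4.2 defines the Safety set as enrolled, treated patients with any post-baseline data. It adds: "The safety population will be used in all safety analyses".
- SAP 7.1 repeats the rule: "Analysis of the efficacy endpoints (primary, secondary, and exploratory) will be based on the ITT population defined in Section 4.1". It makes the matching statement for safety.

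On context, SAP 3.1 states: "This is an open-label safety study of stereotactic, intracranial injection of SB623 cells". SAP 7.5 plans an interim analysis once the last patient reaches Month 6: "This interim analysis will be based on the Month 6 data and will include all tables, listings, and figures". Month 6 is the primary efficacy time point (SAP 6.1).

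**The concern.** A set defined as all enrolled patients and used in all efficacy analyses cannot also be a set from which the sponsor removes patients. The same holds for safety. One of the two rules must give way, and the SAP does not say which.

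The open-ended test matters because the patients' results are visible. With one treatment and no blinding, whoever judges whether a deviation damages interpretation can know how that patient fared. If 7.2.3 means the final lock, the complete Month 6 output would already exist when exclusions are decided.

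At stake is which patients and values enter the main efficacy results. For safety, the primary objective, 7.2.3 as written could take a treated patient out of the summary tables.

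**Working it through.** **1. Can the sections be reconciled?** One reading would let 7.2.3 act only on a supplementary set. Protocol 18.2.1 says the SAP will define an Evaluable population, but SAP section 4 defines only ITT and Safety. Exclusions under 7.2.3 therefore have no other set to act on. SAP 9.3 also plans Listing 16.2.17, for patients excluded from the primary efficacy analyses, while SAP 7.3.1 runs those analyses on ITT. The SAP thus foresees removals from the ITT analysis, and the conflict is not one stray sentence.

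**2. The plan's own figure.** SAP 3.3 and Protocol 18.5 state a chance below 5% of missing a dose-limiting toxicity with 6 patients per cohort at a true rate of 40%. The formula is (1 − 0.4)^n.

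- n = 6: 0.6^6 = 4.67%, which reproduces the statement.
- n = 5: 0.6^5 = 7.78%.
- n = 4: 0.6^4 = 12.96%.

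A safety summary that omitted even one patient of a cohort would no longer carry the stated assurance. This applies only to such a summary, not to the listings or the Data Safety Monitoring Board's review.

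**3. Efficacy test with nobody excluded.** Inputs are n = 18 (SAP 3.3) and the Wilcoxon signed-rank test at two-sided 0.05 (SAP 7.3.1). Under no true change, the exact chance of p < 0.05 in the direction of improvement is:

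| Patients analysed | 18 | 17 | 16 | 15 |
|---|---|---|---|---|
| Exact rate | 2.41% | 2.24% | 2.22% | 2.40% |

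**4. All deviating patients dropped, outcome ignored.** Let each patient deviate independently with probability q, so the number deviating, m, is Binomial(18, q). The rate is the sum over m of P(m) × size(18 − m). This gives 2.30% at q = 10%, 2.33% at 20% and 2.28% at 30%. Exclusion as such does not raise the error rate.

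**5. Exclusions guided by outcome.** Deviating patients are dropped in order from the lowest change. A trial counts as favourable if p < 0.05 is reached with any number of exclusions from 0 up to the cap. The simulation used 1,000,000 trials with standard normal changes and no ties (Monte Carlo standard error below 0.03 percentage points; simulated rate without exclusions 2.39%).

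| Assumed deviation rate | Up to 1 | Up to 2 | Up to 3 |
|---|---|---|---|
| 10% | 3.2% | 3.5% | 3.6% |
| 20% | 3.9% | 4.8% | 5.2% |
| 30% | 4.4% | 6.1% | 7.4% |

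These figures hold for one endpoint and at most three exclusions. Without that cap, the 30% row reaches about 8%. The documents give no deviation rate, so the three rates are assumptions. Comparing steps 4 and 5 shows that the harm comes from knowledge of outcome, not from the smaller sample.

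**The case against.** The strongest reply has four parts.

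- **Efficacy is exploratory.** SAP 7.1.1 states: "All efficacy evaluations are exploratory and no adjustment for multiplicity will be performed". The plan does not claim the false-positive control that the simulation measures, and at a 10% deviation rate the rise is only from 2.4% to 3.6%. This stands, and it limits the severity. Tests at two-sided 0.05 are nevertheless planned and will be read.
- **Timing offers some control.** The decision precedes a lock. The Month 6 output includes all listings, hence Listing 16.2.17, so Month 6 exclusions may naturally be settled by then, and a later exclusion would show against that output. This is a reasonable inference, but SAP 7.5 names no lock. Even on that reading, an open-label decision need not be made without sight of outcomes.
- **Exclusions leave a trail.** All deviations are listed, population counts are tabulated by cohort (SAP 7.2.1), and Protocol 18.6 requires departures from the protocol's planned analysis to be explained. This stands as disclosure. None of it restores a patient to the main analysis, and no listing is titled for safety exclusions or excluded single values.
- **Safety is largely protected.** SAP 7.4 evaluates safety for all patients in the Safety population. Board review (SAP 7.6) and the listings of adverse events, dose-limiting toxicities, serious events and deaths (SAP 7.4.1) are not shown to be affected. This stands. What is exposed is the summary tables.

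It is also fair to say that no document shows an exclusion being made. The 2016 addendum concerns Fugl-Meyer scoring and mentions none.

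**Conclusion.** The concern holds. The contradiction between SAP 7.2.3 and SAP 4.1, 4.2 and 7.1 is certain on the text, and the criterion for exclusion is open-ended. The consequence for efficacy is moderate: from 2.4% to between 3.2% and 7.4% under the assumed deviation rates, with outcome-guided selection, one endpoint and at most three exclusions, and no increase at all if exclusions ignore outcome. For safety, the finding is a wording conflict that needs reconciling. The defect is the permission itself; there is no evidence that it was used. The change should be made, as the conflict is clear and the repair is cheap.

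**What to change.** 1. Amend SAP 7.2.3 so that protocol deviations do not remove patients or values from the ITT and Safety analyses. The one exception would be measurements documented as technically invalid without reference to outcome.
2. Define the Evaluable set that Protocol 18.2.1 leaves to the SAP, and report deviation-based exclusions only there, as a sensitivity analysis.
3. Fix the qualifying deviation types before the relevant data are tabulated, and name the database lock that is meant.
4. Extend Listing 16.2.17 to safety exclusions and excluded single values, with reasons.

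The December 2016 addendum describes analyses in the past tense and refers to final data, so tabulation may already have happened. In that case, report the ITT and Safety results as the main results and label any exclusion set post hoc.

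The cost is SAP wording, one sensitivity table and an extension of one existing listing. Tables need rerunning only where patients or values were in fact excluded. The small downside is that values affected by deviations stay in the main analysis.

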7.2.4 Treatment Exposure

Using the surgical and implantation procedures as described in Protocol Section 6.0, and preparation and administration as described in Protocol Section 11.4, one burr hole will be made in the skull of the patient in a location that will allow ready access to the infarct region. Cells will be implanted using 3 needle tracks with 5 cell deposits for each track at varying depths. Cell implantation will be standardized as to volume (20 μ L/deposit) and rate (10 μ L /min), with spacing between each implant of approximately 5-6 mm.

Data that are collected and related to cell administration will be listed.

7.2.5 Concomitant Medications

All concomitant medications including prescription and over-the-counter drugs taken during the 14 days prior to enrollment or used anytime during the study through 2 years post study treatment administration will be documented. Documentation (through month 9 only) will include changes from the prior visit, start and stop dates, dose, and reasons for the medication use. Concomitant medication data will be coded using World Health Organization Drug Dictionary (WHODD) September 2012 (or later). All concomitant medication data will be summarized by anatomical therapeutic class (ATC) and preferred name with ATC.

A listing of all concomitant medications and nondrug therapies will be included.

This Document is Company Confidential Page 13 of 28

7.2.6 Medical History

Medical history will include significant medical conditions, diagnosis and/or surgical history occurring prior to informed consent or changes occurring between signing of informed consent and study treatment administration. Medical history events will be classified based on the MedDRA dictionary, version 15.1 (or higher), and summaries will be based on preferred term and system organ class (SOC).

A listing of all medical history will be provided.

7.2.7 Ischemic Stroke History

Ischemic stroke history will include date and cause of stroke, date confirmed if by CT or MRI, and location/size (volume in cc) of the affected brain region or changes occurring between signing of informed consent and study treatment administration.

A listing of ischemic stroke history will be provided.

7.2.8 Signs and Symptom History

Baseline signs and symptoms will include a general survey of impairment at baseline or changes occurring between signing of informed consent and study treatment administration. Categories of impairment include, but are not limited to; difficulty reading, difficulty writing, difficulty speaking, difficulty swallowing, incontinence.

A listing of signs and symptom history will be provided.

7.2.9 12-Lead ECG and Chest X-Ray

A listing of all baseline ECG values will be provided. A listing of baseline chest x-ray results will also be provided.

7.2.10 Occult Malignancy Tests

A listing of all occult malignancy tests (hemoccult, chest x-ray finding, carcinoembryonic antigen (CEA) level, prostate-specific antigen level, CA-125 level, alpha-fetoprotein (AFP) level, and beta-HCG level), test date, and the results will be provided.

7.3 EFFICACY ANALYSES FOR EACH COHORT AND COMBINED COHORTS

7.3.1 Primary Efficacy Analyses

The primary clinical analysis will be a pooled analysis of change from baseline at 6 months for ESS total score and motor function total score, using the ITT population as defined in Section 4.1. The primary radiographic analysis will be a pooled analysis of change from baseline at 6 months in FDG uptake as measured by PET scan, using the ITT population.

Wilcoxon Signed Rank test for change from baseline of each endpoint will be independently assessed using a two-sided significance level of 0.05, without correction for multiplicity.

A listing of ESS scores and FDG-PET parameters, including dates of MRI and CT scans, will be included.

7.3.2 Secondary Efficacy Analyses

The secondary clinical analyses will be pooled analyses of changes from baseline at 6 months for NIHSS total score, motor function total score and motor function upper and lower extremity score; MRS scalar assessment; Fugl-Meyer total score, motor function total score and motor function upper and lower extremity score; and cognitive status using the ITT population.

Wilcoxon Signed Rank tests for change from baseline of each endpoint will be independently assessed using a two-sided significance level of 0.05, without correction for multiplicity.

Listings of NIHSS, MRS, Fugl-Meyer Scores and Cognitive Function Test assessment results will be included.

7.3.3 Exploratory Efficacy Analyses

The exploratory clinical analyses will be pooled analyses of changes from baseline at 1, 2, 3, 4, 9, 12, and 24 months for ESS total score and motor function total score; NIHSS total score, motor function total score and motor function upper and lower extremity score; MRS scalar assessment; and Fugl-Meyer total score, motor function total score and motor function upper and lower extremity score. Pooled analyses of changes from baseline at 12 and 24 months will be conducted for Cognitive Tests and FDG-PET uptake. Exploratory analysis of FDG-PET tissue ratio at 6, 12, and 24 months will also be included. All exploratory analysis will use the ITT population. Inferential tests for change from baseline of each endpoint at each visit will be independently assessed using a two-sided significance level of 0.05.

A mean change from baseline by visit results for the ESS total score; NIHSS total score, motor function total score, and motor function upper and lower extremity score of affected side; MRS scalar assessment; Fugl-Meyer total score, motor function total score, and motor function upper and lower extremity score; and FDG-PET uptake will be graphically presented by individual dose and pooled dose.

7.4 SAFETY ANALYSES FOR EACH COHORT AND COMBINED COHORTS

Incidence of adverse events, dose-limiting toxicities, serious adverse events, clinically significant changes in laboratory data, physical exam, and vital signs, changes in head MRI exams, antibody development, and changes in PBMC function will be analyzed to evaluate the safety of SB623 for all patients in the safety population through 2 years post study treatment administration.

Physical exam and vital sign data, absolute and change from baseline, will be listed by patient by visit. Laboratory data values falling above or below normal range and considered clinically significant will be indicated on the corresponding laboratory listings. Any changes in MRI images at visits post study treatment administration will be indicated in the MRI listing. Presence of antibodies to SB623 (see Section 7.4.6) will be indicated in the antibody listing by patient by visit. PBMC function, the cytokine measurements, will be listed by patient by visit. Descriptive statistics for absolute and change from baseline values will be displayed for each continuous laboratory parameter at each time point.

This Document is Company Confidential Page 15 of 28

7.4.1 Adverse Events

A treatment-emergent adverse event (TEAE) is defined as any event not present prior to study treatment administration or any event already present that worsens in either intensity or frequency following exposure to study treatment.

Adverse events will be classified based on the Medical Dictionary for Regulatory Activities (MedDRA) dictionary, version 15.1 (or higher). Analyses will be conducted on preferred term and primary system organ class (SOC). All adverse event data will be listed per patient including severity, relationship to study treatment, and action taken. Event severity is based on the World Health Organization (WHO) standard toxicity criteria (STC).

A Dose-limiting toxicity (DLT) will be defined as any grade 3 or 4 event which is at least possibly related to study product or administration procedure.

The adverse event reporting period for this trial begins upon receiving the dose of study treatment and ends 24 months after the administration of SB623.

The following summaries of AEs will be provided:

- TEAEs by MedDRA SOC and by preferred term
- TEAEs by maximum severity (mild, moderate, severe, life-threatening) by MedDRA SOC and preferred term
- TEAEs by relationship to study treatment by not related (includes unrelated and unlikely related) or related (includes possibly, probably, and definitely related) by MedDRA SOC and preferred term.
- AEs resulting in discontinuation from the study, by MedDRA SOC and preferred term
- SAEs by MedDRA SOC and preferred term
- The following listings of adverse events will be provided (TEAEs will be denoted in each listing):
 - o All AEs
 - All Dose-Limiting Toxicities (DLTs)
 - o Adverse events resulting in discontinuation from the study
 - o Deaths (if any)
 - o Serious adverse events
 - AE mappings to MedDRA dictionary terms

